6.4.4 Treatment by Center Effect

The randomization in this study is stratified by prior exposure to biologic therapy (i.e., biologic-naïve vs. biologic-experienced subjects) and body weight (i.e., <90 kg vs. \geq 90 kg at Visit 2). Center effect is not considered due to the expectation that many centers will be used and only a small number of subjects will be enrolled in most centers.

6.4.5 Treatment by Baseline Covariate Effect

The treatment-by-baseline effect will be assessed as appropriate. The baseline will be included in the respective parametric analysis model of the efficacy parameters where appropriate.

6.4.6 Subgroup Analysis

As exploratory analyses, further subgroup analyses may be conducted for selected parameters. The subgroups that may be examined include, but are not limited to, the following:

- Prior biologic therapy (naïve vs. experienced)
- Body weight (<90 kg vs. \geq 90kg at Visit 2)

6.4.7 Handling of Dropouts and Missing Data

There may be missing data intermittently (e.g., a missing visit or subject dropout). For PASI-50/-75/-90 and sPGA (achieving score of 0 or 1) responses, subjects with missing EOT data will be imputed as non-responders at EOT; for analyses by scheduled time points, missing data will not be imputed. For analysis with multiple time points, any missing data will be imputed using the last observation carried forward (LOCF) method. For parameters analyzed both by time point and with multiple time points, these two approaches would strengthen the findings when they are similar.

For efficacy analysis of continuous parameters, missing data will not be imputed. This is because the statistical models employed (e.g., mixed effect model) generally provide valid estimates if the missing data mechanism is so-called “missing at random,” a common assumption made as the first approach for analysis.

For the Itch NRS, 4 completed days are necessary to derive a weekly score (1-3 missed days, consecutive or non-consecutive, are allowed). Any missing individual items are treated as missing data. When a weekly score in post-dose time point cannot be calculated (less than 4 completed days), the time point will not be included in the analysis. If a baseline weekly score cannot be derived (i.e., less than 4 completed days from Day -6 to Day 1), the Itch NRS score of the subject will not be included in the analysis.

For the Skindex-16, if more than 25% of the responses are missing, the scale is considered missing. An item with multiple answers is considered missing. The skindex-16 score will be derived for all study visits.

Additional sensitivity analyses of the primary efficacy parameter, i.e., PASI-75 at EOT, may be performed using other missing data handling procedures or approaches.

6.5 Safety Analysis

All safety analyses will be summarized based on the Safety population.

Potentially clinically significant (PCS) abnormalities will be defined according to the Akros Safety Reporting Standards as of 18 Oct, 2004. The PCS values for vital signs, ECG and laboratory data will be flagged in data listings.

Treatment-emergent PCS abnormalities are values that meet the specified criteria after the initiation of study drug (see Section 10.1 for detailed clinically significant criteria).

Treatment-emergent PCS values will be summarized, presenting the number and percentage of subjects who had at least one PCS value on or after the first dose of study drug (JTE-451 or placebo). The denominator is always the number of subjects in the safety population, regardless of whether the subject had any post-baseline measurements. The numerator is the number of subjects in the safety population with any PCS value in the treatment-emergent period. Note that for the purpose of determining PCS abnormalities, baseline is always the last non-missing value before the first dose of study drug. As all procedures will be performed before dosing at each scheduled visit, the values of the scheduled Day 1 collection will be baseline and will not be treatment-emergent PCS.

All safety data will be presented in the data listings, and will be flagged for events of interest (e.g., out of range laboratory data) as appropriate.

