6.5.4 Clinical Laboratory Tests

Descriptive statistics of observed results and change from baseline for hematology, serum biochemistry, coagulation and continuous urinalysis will be presented by time point and treatment group. Frequency and percentage of the distribution of discrete urinalysis tests will be presented by time point. Number and percentage of subjects with treatment-emergent PCS abnormal values will be summarized by treatment group.

The number and percentage of subjects with post-baseline abnormalities in liver tests will be summarized by treatment group according to [Table 3](#).

Table 3. Criteria for Categorical Analysis in Liver Tests

Parameter	Specified Value			
ALT	ALT \geq ULN \times 3	ALT \geq ULN \times 5	ALT \geq ULN \times 10	ALT \geq ULN \times 20
AST	AST \geq ULN \times 3	AST \geq ULN \times 5	AST \geq ULN \times 10	AST \geq ULN \times 20
ALT and AST	ALT and AST \geq ULN \times 3	ALT and AST \geq ULN \times 5	ALT and AST \geq ULN \times 10	ALT and AST \geq ULN \times 20
ALT or AST	ALT or AST \geq ULN \times 3	ALT or AST \geq ULN \times 5	ALT or AST \geq ULN \times 10	ALT or AST \geq ULN \times 20
T-Bil	T-Bil $>$ ULN \times 1.5		T-Bil $>$ ULN \times 2	
ALP	ALP $>$ ULN \times 1.5			
ALT and T-Bil	ALT \geq ULN \times 3 and T-Bil \geq ULN \times 1.5		ALT \geq ULN \times 3 and T-Bil \geq ULN \times 2	
AST and T-Bil	AST \geq ULN \times 3 and T-Bil \geq ULN \times 1.5		AST \geq ULN \times 3 and T-Bil \geq ULN \times 2	
ALT, AST, ALP and T-Bil	ALT \geq ULN \times 3, AST \geq ULN \times 3, ALP \geq ULN \times 2 and T-Bil \geq ULN \times 2			
ALT and AST	ALT or AST $>$ ULN \times 3 at any treatment visit and any of the following AEs: Nausea, Vomiting, Anorexia, Abdominal pain or Fatigue, reported within +/- 14 days of the abnormal AT values.			

Other clinical laboratory tests (e.g., drug abuse, alcohol screen, viral serology, pregnancy) will be listed in the data listings.

Qualitative urine parameters are generally reported by a descriptive score, which may differ between laboratories. For pooling the data, the qualitative results will be mapped to a four-point scale. A clinical review will be performed on the mapping of the descriptive scores to the four-point scale; and the descriptive scores will be remapped where appropriate. The four-point scale will be used in the determination of the PCS abnormalities.

The mean profile may be presented for selected laboratory parameters.

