10. APPENDICES

10.1 General Clinically-Significant Criteria for Safety Parameters

Parameter (Full Names)	Reporting Unit	Clinically Significant Criteria ¹	
		Low	High
Hematology			
Hematocrit	%	Male ≤37% Female ≤32%	NA
Hemoglobin	g/dl	Male ≤11.5 Female ≤9.5	NA
White blood cell	E3/mm ³	≤2.8	≥16.0
Platelets	E3/mm ³	≤75	≥700
Mean corpuscular hemoglobin	pg/cell	--	--
Mean corpuscular hemoglobin concentration	g/dl	--	--
Mean corpuscular volume	fL	--	--
Red blood cell	E6/mm ³	≤3.5	NA
Differential			
Bands or (Band neutrophil (stab))	%	NA	≥10%
Basophil (absolute)	E3/mm ³	NA	≥0.4
Basophil (%)	%	NA	≥5%
Lymphocytes (absolute)	E3/mm ³	≤0.5	≥4.5
Lymphocytes (%)	%	≤10%	≥80%
Monocytes (absolute)	E3/mm ³	NA	≥1.5
Monocytes (%)	%	NA	≥ 20%
Neutrophils (absolute)	E3/mm ³	≤1.0	
Neutrophils (%)	%	≤15%	≥90%
Eosinophils (absolute)	E3/mm ³	NA	≥0.7
Eosinophils (%)	%	NA	≥10%
Coagulation			
Prothrombin time	seconds	NA	≥16
International Normalized Ratio	ratio	NA	≥2.00
Partial thromboplastin time	Seconds	NA	≥50

¹ Can be revised as appropriate, but should be consistent within the project.

Parameter (Full Names)	Reporting Unit	Clinically Significant Criteria ¹	
		Low	High
Heart Function			
Aspartate transaminase	IU/l	NA	≥3 x UNL
Lactic dehydrogenase	U/L	NA	≥3 x UNL
CPK (MB Fraction)	µg/L	--	--
Liver Function			
Alkaline Phosphatase	IU/l	NA	≥3 x UNL
Alanine transaminase	IU/l	NA	≥3 x UNL
Total Bilirubin	mg/dl	NA	≥2.0
Gamma-glutamyltransferase	IU/l	NA	≥3 x UNL
Total Protein	g/dl	≤4.5	≥9.0
Albumin	g/dl	≤2.5	≥6.5
Renal Function			
Blood urea nitrogen	mg/dl	NA	≥30
Creatinine	mg/dl	NA	≥2.0
Thyroid Function			
T ₃ Uptake, total	nmol/L	--	--
Reverse T ₃	nmol/L	--	--
Thyroxine (T ₄)	nmol/L	--	--
Human chorioic gonadotropin	IU/L	--	--
Free T ₄	pmol/L	--	--
Thyroid- stimulating hormone	mU/L	--	--
Follicle- stimulating hormone	--	--	--
Lipid Chemistry			
Total cholesterol	mg/dl	NA	≥300
LDL cholesterol	mg/dl	--	--
HDL cholesterol	mg/dl	--	--
Ratio (LDL/HDL)	Fraction	--	--
Triglycerides	mg/dl	NA	≥300

Parameter (Full Names)	Reporting Unit	Clinically Significant Criteria ¹	
		Low	High
Electrolytes			
Chloride	MEq/l	≤90	≥112
Potassium	MEq/l	≤3.0	≥5.8
Sodium	MEq/l	≤130	≥150
Bicarbonate	MEq/L	--	--
Metabolic			
Calcium	mg/dl	≤7.0	≥15.5
Phosphate	mg/dl	≤1.5	≥6.0
Blood Glucose	mg/dl	≤50 (fasting)	≥180 (fasting)
Uric Acid	mg/dl	NA	Male ≥10.5 Female ≥8.5
Cancer			
Prostate-specific antigen	--	--	--
Alpha-fetoprotein	--	--	--
Viral tests			
HIV	--	--	--
HIV ₂	--	--	--
Hepatitis A virus	--	--	--

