Hepatitis A antibody	--	--	--
Hepatitis B virus	--	--	--
Hepatitis B surface Antigen	--	--	--
Hepatitis B core antigen	--	--	--
Hepatitis C virus	--	--	--
Urinalysis			
(Urine) protein		NA	Increase≥2
(Urine) glucose		NA	Increase≥2
(Urine) bilirubin		NA	Increase≥2
Occult blood		NA	Increase≥2
Color		NA	Increase≥2
Ketone		NA	Increase≥2
Leukocyte esterase		NA	Increase≥2
pH		Decrease≥2	Increase≥2
Turbidity		NA	Increase≥2
Urobilinogen		NA	Increase≥2
Specific gravity		≤1.005	NA

¹ Can be revised as appropriate, but should be consistent within the project.

Parameter (Full Names)	Reporting Unit	Clinically Significant Criteria ¹	
		Low	High
Vital Sign			
Systolic blood pressure	mmHg	≤90 and ≥20 decrease	≥180 and ≥20 increase
Diastolic blood pressure	mmHg	≤50 and ≥15 decrease	≥105 and ≥15 increase
Pulse rate	bpm	≤50 and ≥15 decrease	≥120 and ≥15 increase
Body Temperature	C°	NA	≥1.11 C° Increase
Respiration rate	#/min	≤ 10	--
Height	cm	--	--
Weight	kg	≥7% decrease	≥7% increase
Body mass index	kg/m ²		
Hip Circumference	cm		
Waist Circumference	cm		
ECG			
Heart rate	bpm	<50	>100
R-R interval	msec	--	--
PR interval	msec	NA	>200 msec and >Baseline
QRS interval	msec	NA	>120 msec and >Baseline
QT interval	msec	NA	>450 and >30 increase
QTc interval	msec	<=350 and Baseline<375	>450 or >480 or >500 with Baseline <450
QTc interval ¹	msec	NA	>30 increase or >60 increase

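### SAP 6.5 counts unchanged pre-existing abnormalities as treatment-emergent PCS in the 41 of 61 criterion rows without a baseline condition (about 35 exposed in practice)

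*SAP*

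**What the plan says.** SAP 6.5 sets the rule: "Treatment-emergent PCS abnormalities are values that meet the specified criteria after the initiation of study drug". The numerator is every subject with any such value in the treatment-emergent period, and the denominator is the whole safety population. The scheduled Day 1 value is treated as baseline and is not itself counted. The section also states that "for the purpose of determining PCS abnormalities, baseline is always the last non-missing value before the first dose of study drug".

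The limits are listed in SAP 10.1. Some rows refer to baseline, for example PR interval, ">200 msec and >Baseline". Most laboratory rows are absolute cut-offs, for example haemoglobin, "Male ≤11.5 Female ≤9.5".

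SAP 6.5.4 says "Number and percentage of subjects with treatment-emergent PCS abnormal values will be summarized by treatment group", and 6.5.5 and 6.5.6 plan the same for vital signs and ECG. None of the three names a table of baseline against post-baseline category. SAP 6.5 also refers to a source outside the SAP: "Potentially clinically significant (PCS) abnormalities will be defined according to the Akros Safety Reporting Standards as of 18 Oct, 2004".

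**The concern.** The label tells the reader that the abnormality arose on treatment. The rule removes the Day 1 value but not the same value at the next visit. Take a subject with triglycerides of 320 mg/dL on Day 1 and 320 mg/dL at Week 2, against a limit of 300 mg/dL. That subject is not counted on Day 1 but is counted at Week 2.

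This differs from the SAP's own use of the term for adverse events. SAP 5.3.3 counts an event present before treatment only if it worsened, or if it recovered and then recurred. It also gives one label two meanings within the PCS tables, because rows with a change condition measure something closer to new onset.

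What is at stake is how the PCS incidence tables are read. Carried-over abnormalities raise the count in every arm and pull the active-to-placebo ratio toward 1. No test uses these tables, and the TEAE and change-from-baseline summaries are untouched.

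**Working it through.** **Step 1: classify the rows of SAP 10.1.** A row counts if its Low or High cell holds a limit.

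- No baseline or change condition: 5 haematology + 11 differential + 3 coagulation + 2 heart + 6 liver + 2 renal + 2 lipid + 3 electrolyte + 4 metabolic + urine specific gravity + respiration rate + ECG heart rate = **41**.
- With such a condition: 10 urinalysis + 5 vital signs (systolic and diastolic pressure, pulse, temperature, weight) + 5 ECG (PR, QRS, QT, two QTc rows) = **20**.
- Total 61; 41/61 = 67%. One QTc cell can be read with its baseline clause applying only to the last of its three limits. On that reading the count is 42.

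**Step 2: remove rows with little practical exposure.**

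- Band neutrophils and ECG heart rate are not among the parameters named in Protocol 3.5.6.13 and SAP 6.5.6: minus 2.
- ALT and AST above 2 × ULN are excluded at Visit 1 (PCS limit 3 × ULN), as are absolute neutrophils below 1.5 (PCS limit 1.0): minus 3.
- Creatinine above 1.5 × ULN is excluded. This is stricter than the PCS limit of 2.0 mg/dL if the ULN is below 2.0/1.5 = 1.33 mg/dL. The ULN is not given, so this is an assumption: minus 1.
- 41 − 2 − 3 − 1 = **35**.

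The 35 is a judgement; 35 to 41 is defensible. Eligibility is checked at Visit 1, up to 28 days before Day 1, so screened rows are not fully closed. Conversely, some of the 35 are only partly open:

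- Leucocytes, platelets and absolute lymphocytes are open only on the high side.
- Haemoglobin is open essentially only for men at 11.0 to 11.5 g/dL.
- Low neutrophil percentage is largely closed: an absolute count of at least 1.5 with 15% or less needs leucocytes of at least 1.5/0.15 = 10.0.
- Glucose and haematocrit are limited only indirectly, by the HbA1c and haemoglobin exclusions.

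Triglycerides, total cholesterol, GGT, uric acid, eosinophils and urine specific gravity have no visible numeric entry limit.

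**Step 3: size of the effect.** The documents state no figure to reproduce, so the inputs are assumptions for one exposed parameter. Let p be PCS prevalence at baseline, s the share of those still PCS later (equal in both arms) and r new onset among the rest (0.04 placebo, 0.12 active). The denominator is the safety population, 50 per arm.

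- As written: p·s + (1 − p)·r
- With a baseline condition: (1 − p)·r
- Carried-over subjects per arm: 50·p·s

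For p = 0.05 and s = 0.8, p·s = 0.040:

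- placebo 0.040 + 0.95 × 0.04 = 0.078
- active 0.040 + 0.95 × 0.12 = 0.154
- with the fix, 0.038 and 0.114

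| p, s | As written, placebo / active | Ratio | With fix, placebo / active | Ratio | Difference (both) | Carried over per arm | Carried-over share, placebo / active |
|---|---|---|---|---|---|---|---|
| 0.02, 0.5 | 4.92% / 12.76% | 2.59 | 3.92% / 11.76% | 3.0 | 7.84 points | 0.5 | 20% / 8% |
| 0.05, 0.8 | 7.8% / 15.4% | 1.97 | 3.8% / 11.4% | 3.0 | 7.6 points | 2.0 | 51% / 26% |
| 0.10, 1.0 | 13.6% / 20.8% | 1.53 | 3.6% / 10.8% | 3.0 | 7.2 points | 5.0 | 74% / 48% |

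The expected difference does not move, but its sampling error does. In the middle row the standard error is √[(0.078 × 0.922 + 0.154 × 0.846)/50] = 6.4 points as written and √[(0.038 × 0.962 + 0.114 × 0.886)/50] = 5.2 points with the fix.

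**The case against.** The strongest reply is that this is a stated convention, not a mistake. SAP 6.5 says what it counts, the baseline definition is needed for the 20 rows that use it, and the timing-only count keeps subjects who start abnormal and get worse. The SAP plans counts and percentages, not ratios, and the expected difference between arms is unchanged. The prevalences are assumed, and 2-10% is unlikely for extreme limits such as calcium of 15.5 mg/dL or platelets of 700. The 35 rows also overlap, since cell types appear as both absolute and percentage values.

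There are other safeguards. Exclusion criterion 26 lets the investigator keep out relevant laboratory abnormalities. Clinically significant abnormal results are recorded as adverse events, where the definition does take account of the prior state. SAP 5.3.6 derives low, normal and high classes and change from baseline. Finally, the 2004 standard could hold a baseline rule, exclusion criteria 1 and 2 are redacted, and the mock tables are in a separate document.

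Much of this limits the size of the problem, and it is why the point is minor. It does not remove it. Criterion 26 is discretionary. Normal-range classes and mean changes do not count subjects who newly cross a PCS limit. Listings flag the values, so new-onset counts could be rebuilt, but no table named in the SAP gives them. The unseen documents remain a real uncertainty, yet SAP 6.5 states its own definition and that definition has no baseline rule. The loss of subjects who worsen from an abnormal baseline is a fair criticism of a bare new-onset rule, and a shift table answers it.

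**Conclusion.** The concern holds, as a minor point. Followed as written, SAP 6.5 counts unchanged pre-existing abnormalities as treatment-emergent in 41 of 61 criterion rows, about 35 of them with practical exposure. Under the illustrative assumptions, 0.5 to 5 subjects per arm of 50 are carried over per exposed parameter. They form 20-74% of the placebo count, and a ratio of 3.0 appears as 2.6 down to 1.5. For rows protected by entry criteria the effect is near zero.

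With equal persistence in both arms there is no directional bias and the expected risk difference is unchanged. No efficacy result or test is involved. Confidence is medium, because the 2004 standard, the redacted exclusion criteria and the mock tables could not be seen.

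**What to change.** - In SAP 6.5, for criteria without a baseline condition, count a post-baseline value as treatment-emergent PCS only if the baseline value for that parameter and direction did not meet the criterion, or is missing.
- In 6.5.4 to 6.5.6, add a table of baseline against worst post-baseline category, so that subjects who are PCS at baseline and worsen stay visible.
- Keep every PCS value flagged in the listings.
- If the 2004 standard already holds a baseline rule, state it in 6.5.
- If the timing-only count is kept, title it post-baseline PCS, in line with the liver-test wording in 6.5.4: "The number and percentage of subjects with post-baseline abnormalities in liver tests will be summarized by treatment group".

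The cost is one sentence, one derivation flag and one table layout repeated for laboratory, vital-sign and ECG parameters, all on data already collected. The 10.1 footnote allows the change: "Can be revised as appropriate, but should be consistent within the project". It also asks for consistency, so the same rule should be applied in sister studies before pooling. The incidence table must then be read together with the shift table. Relabelling alone costs almost nothing but leaves new-onset counts untabulated.

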Subjects will be administered the first dose of study drug at the site, upon completion of all pre-dosing procedures and randomization at Visit 2; subsequently, they will be instructed to self-administer study drug BID, at approximately 12-hour intervals, regardless of meals. However, subjects should not take study drug on the day of a study visit until after all study procedures have been completed (except for post-dose PK samples collection as shown in [Figure 2](#)). On study visit days, subjects should take their scheduled study treatment at the site, under the supervision of the investigator or designee after all required procedures prior to administration have been performed (except for Visit 7, when no study drug will be administered, as the last dose will be taken the day prior to the visit). If the subject inadvertently took study drug on the day of the study visit, prior to all required procedures, he/she may complete the visit and the actual date and time of the last dose prior to the PK blood samples collection will be accurately recorded.

Exact date and time of the last two doses prior to the pre-dose/trough PK sample collection at Visits 4 through 7 and the dosing time at the site should be documented at each visit during the Treatment Period (i.e., Visits 2 through 6).

Study drug will not be administered and all remaining study drug will be collected from the subjects at Visit 7.

If a subject discontinues the study prematurely after receiving at least one dose of study drug, an Early Termination Visit should be completed at which all procedures listed for the Visit 7 should be performed, if possible, prior to any changes made in the subject's anti-psoriasis therapy.

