4. SUBJECT POPULATIONS

4.1 Safety Population

The safety population consists of the randomized subjects who receive at least one dose of the study drug.

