6.1 Sample Size

Approximately 150 eligible subjects (50 subjects in each treatment group) will be randomized into the double-blind treatment period.

The sample size estimation is based on the primary efficacy parameter of the proportion of subjects achieving PASI-75 at EOT.

Taking into consideration a 15-20% treatment discontinuation rate, about 50 subjects per group will be randomized into the double-blind treatment period.

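### SAP 6.5 divides PCS counts by all treated subjects, so anyone with no post-baseline value counts as normal and rates may be slightly understated

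*SAP*

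**What the plan says.** SAP 6.5 defines both halves of the PCS percentage. For the denominator: "The denominator is always the number of subjects in the safety population, regardless of whether the subject had any post-baseline measurements". For the numerator: "The numerator is the number of subjects in the safety population with any PCS value in the treatment-emergent period". The same section adds that "the values of the scheduled Day 1 collection will be baseline and will not be treatment-emergent PCS", so only a later measurement can put a subject in the numerator.

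Entry to the population requires dosing and nothing more (SAP 4.1): "The safety population consists of the randomized subjects who receive at least one dose of the study drug".

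SAP 6.5.4 to 6.5.6 then call for numbers and percentages of subjects with treatment-emergent PCS values for laboratory, vital-sign and ECG data. None of them gives another denominator, and no sensitivity analysis for unmeasured subjects is planned.

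Some criteria in SAP 10.1 depend on the baseline value. The QTc row, for example, reads ">450 or >480 or >500 with Baseline <450".

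**The concern.** A laboratory or ECG abnormality exists in the data only if somebody took the measurement. Adverse events are different: they are recorded whenever site staff learn of them, so dividing by everyone treated is natural there. Carried over to PCS values, the same denominator gives an unmeasured subject the favourable result. The efficacy rule in SAP 6.4.7 goes the other way, since a missing PASI or sPGA response at end of treatment is set to non-response.

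ECG is the most exposed parameter. Laboratory and vital-sign data are first due after baseline at Week 2, but the first post-baseline tracing is at Week 4, and only one more is scheduled after that. If early leavers without a tracing are more frequent in one arm, that arm's PCS percentage is pulled down further than the other's.

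A related dilution comes from baseline-dependent criteria. A subject whose baseline QTc rules out the criterion stays in the denominator. So does a subject already in the top two categories of the four-point urine scale of SAP 6.5.4 when the criterion is a rise of two.

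**Working it through.** The plan states no PCS rate and no fraction of unmeasured subjects, so there is no figure of its own to reproduce. The check is algebra followed by illustration.

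**Inputs**
- N = 50 per arm. SAP 6.1: "Approximately 150 eligible subjects (50 subjects in each treatment group) will be randomized into the double-blind treatment period". I assume that all are dosed, so that the safety population per arm is also 50.
- Planned discontinuation of 15% to 20%. SAP 6.1: "Taking into consideration a 15-20% treatment discontinuation rate, about 50 subjects per group will be randomized". This covers all discontinuations over the study, not only those before a first post-baseline value.
- m = fraction of the safety population with no post-baseline value for the parameter. Not in the documents; varied below as an assumption.
- x = subjects with at least one treatment-emergent PCS value; x = 4 is illustrative.

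**Step 1: relation between the two rates**
- Rate under SAP 6.5 = x / N.
- Rate among assessed subjects = x / [N(1 − m)].
- So the SAP rate = assessed rate × (1 − m). The relative understatement is exactly m. It is zero when m = 0, and the SAP rate can never exceed the assessed rate.

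**Step 2: one arm, x = 4, SAP rate 4/50 = 8.0%**
- 0 unmeasured: 4/50 = 8.0%
- 1 unmeasured (m = 2%): 4/49 = 8.2%
- 3 unmeasured (m = 6%): 4/47 = 8.5%
- 5 unmeasured (m = 10%): 4/45 = 8.9%
- Extreme bound, every planned discontinuation at 20% unmeasured: 4/40 = 10.0%

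**Step 3: how plausible are 1 to 5 unmeasured subjects?** Planned discontinuations are 0.15 × 50 = 7.5 to 0.20 × 50 = 10 per arm. Five unmeasured subjects would be 5/10 = 50% to 5/7.5 = 67% of all discontinuations; one would be 1/10 = 10% to 1/7.5 = 13%. The upper end of the range is therefore demanding.

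**Step 4: comparison between arms.** Take the same assessed rate of 10% in both arms and let m differ (assumptions).
- m = 2% on placebo and 10% on active: 10% × 0.98 = 9.8% against 10% × 0.90 = 9.0%, ratio 0.90/0.98 = 0.92.
- m = 4% on placebo and 20% on active (extreme): 9.6% against 8.0%, ratio 0.80/0.96 = 0.83.

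With equal m the ratio is unaffected, because the factor (1 − m) cancels.

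**The case against.** The rule is an openly declared convention, applied alike to all arms. It keeps the PCS tables on the population used for every other safety summary. SAP 6 also requires each percentage's denominator to be shown and gives the non-missing n in continuous summaries, so a careful reader can see part of the gap. This stands as mitigation. But the denominator shown would still be the full safety N, and the unmeasured subjects would still be counted as normal.

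The unmeasured group is likely to be small. After premature discontinuation, Protocol 3.5.3 says "an Early Termination Visit should be completed at which all procedures listed for the Visit 7 should be performed, if possible", and Protocol 3.4 and 3.5.4 also ask for the Follow-up Visit procedures about 4 weeks after the last dose. SAP 6.5 sets no end date for a treatment-emergent value, so those results count. The schedules, as extracted, place the last ECG under Visit 8 in the protocol and under Visit 7 in the SAP. This may be a table-reading artefact; on either reading a tracing after discontinuation is requested. To be unmeasured for ECG, a subject must leave before Week 4 and also miss that later tracing. This argument stands, and it limits the size of the point.

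The net direction of error in a PCS rate is not settled by the denominator alone. Many laboratory criteria in SAP 10.1 require no normal baseline (triglycerides of 300 mg/dl or more, for instance), so subjects already abnormal can enter the numerator and raise the rate. This is true, but it is a separate feature and does not correct the denominator.

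The assessed-only rate has its own assumption: it describes all treated subjects only if those unmeasured carry similar risk. That also stands, and is a reason to show both percentages.

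Finally, a reader might infer that a safety signal among early leavers would be lost. The documents do not support that. Under Protocol 3.6.1, a laboratory, vital-sign or ECG abnormality that leads to permanent discontinuation is recorded as an adverse event. SAP 6.5.1 tabulates events leading to discontinuation, PCS values are flagged in the listings, and SAP 6.5.4 has a separate liver-test table.

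**Conclusion.** The point holds as a minor one. By the SAP's own wording, a treated subject with no post-baseline value is counted as measured and normal. Relative to assessed subjects, the reported rate is lower by the fraction m, and the comparison between arms shifts only if m differs between them. For 4 PCS subjects in an arm of 50, the difference is 0.2 to 0.9 percentage points if 1 to 5 subjects are unmeasured, and nil if none are. One subject is 2 percentage points at this N, so the effect is less than half a subject.

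Three stronger readings go beyond the documents. The first is that PCS rates are biased downward as a matter of course; this needs m > 0, and m is unknown. The second is that the planned 15% to 20% discontinuation rate estimates m; it is only an extreme upper bound. The third is that the effect is larger for baseline-dependent criteria. The mechanism is real, but the documents do not say how many subjects would have a disqualifying baseline, so its size cannot be given.

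**What to change.** Replace the denominator sentence in SAP 6.5. For each parameter, the denominator should be the safety-population subjects with at least one post-baseline value of that parameter. Where the criterion is conditioned on baseline or measured as a change from it, the subject should also have a baseline value from which the criterion can be met (for example, QTc below 450 where the QTc row requires it). Show n/N in each row and the number not assessed in each arm. The percentage on the full safety population may be kept next to it.

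The cost is one SAP sentence and row-specific denominators in the PCS tables. No new data are needed and trial conduct is unaffected. The downsides are that denominators will differ from row to row, and that a footnote should state that the assessed-only rate extends to all treated subjects only if unmeasured subjects have similar risk.
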